3.1.3 Handling of missed/delayed visits due to COVID-19

Due to the pandemic of Coronavirus Disease 2019 (COVID-19), study visits for some participants may be partially completed, delayed, or cancelled, with the corresponding information collected on the CRF. The sites were given the following instructions:

- If the visit window is exceeded by more than 7 days for the Visit 3 (Day 30) assessment, the visit should be recorded as an unscheduled visit.
- If the visit window is exceeded by more than 14 days for Visit 4 (Day 84), Visit 5 (Day 180), Visit 6 (Day 270), or Visit 7 (Day 365); then the visit should be recorded as an unscheduled visit.

3.1.4 Definition of Baseline

Baseline is defined as the last measurement prior to the first dose of study drug, unless otherwise stated.

3.1.5 Summary Statistics

Categorical data will generally be summarized with counts and percentages of participants. The denominator used for the percentage calculation will be clearly defined. Continuous data will generally be summarized with descriptive statistics including n (number of non-missing values), mean, median, standard deviation, 1st and 3rd quartiles, minimum, and maximum.

3.1.6 Hypothesis Testing

The hypothesis testing of the percentage change in LDL-C from Baseline to Day 84 is statistically defined as:

$$H_0: \mu_1 - \mu_0 = 0, H_1: \mu_1 - \mu_0 \neq 0,$$

where μ_0 - the percentage change in LDL-C in the placebo group,

μ_1 - the percentage change in LDL-C in the obicetrapib group.

A fixed sequential testing procedure will be implemented in order to control the Type I error rate. In a hierarchical step-down manner, the primary endpoint will be tested first, followed by the secondary efficacy endpoints in a pre-specified order (see [Section 3.4.2](#)). No adjustment for multiple comparison will be made for the exploratory efficacy endpoints.

3.1.7 Evaluation of Site Effect

This is a multi-center study. Sites will not be pooled for any planned inferential analysis but may be pooled for subgroup analysis to assess the heterogeneity of treatment effects among pooled sites. The final pooling algorithm, if needed, will be specified before treatment unblinding and will be provided as an addendum to the SAP. Additionally, a review of by-site effects will be performed in the context of data listing review.

3.1.8 *Handling of Dropouts and Missing Data*

The objective is for missing data to be kept to a minimum. Continued efforts will be made to measure endpoints on all participants, including those who may have discontinued study drug. Accordingly, site investigators have been robustly trained about the importance of participant retention and multiple approaches will be implemented to retain participants who fail to actively maintain contact with the investigator.

Date Values

In cases of incomplete dates (e.g., AE, concomitant medication, and medical history start and/or stop dates), the missing component(s) will be assumed as the most conservative value possible. For example, if the start date is incomplete, the first day of the month will be imputed for the missing day and January will be imputed for the missing month. If a stop date is incomplete, the last day of the month will be imputed for the missing day and December will be imputed for the missing month. Incomplete start and stop dates will be listed as collected without imputation.

Date imputation will only be used for computational purposes such as treatment-emergent status. Actual date values, as they appear in the original CRFs, will be presented within the data listings.

Non-Date Values

For sensitivity analyses of the primary efficacy endpoint, missing values will be imputed using multiple imputation methods (see [Section 3.4.1](#)). For the analyses of secondary and exploratory efficacy endpoints, no imputation will be made for missing values. Safety data will be used according to availability, with no imputation for missing data.

3.1.9 *Laboratory Values Above or Below Limits of Quantification*

For laboratory values less than the lower limit of quantification (LLQ), half of the lower limit value (i.e., LLQ/2) will be used in the analysis. For values greater than the upper limit of quantification (ULQ), the upper limit value (i.e., ULQ) will be used in the analyses.

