8.1 Adverse Events

An AE is defined as any untoward medical occurrence in a clinical investigation participant administered a pharmaceutical product, which does not necessarily have a causal relationship with this treatment. An AE can therefore be any unfavorable and/or unintended sign (including an abnormal laboratory finding), symptom, or disease temporally associated with the use of an investigational medicinal product, whether or not related to the investigational medicinal product. All AEs, including observed or volunteered problems, complaints, or symptoms, are to be recorded on the appropriate eCRF.

AEs, which include clinical laboratory test variables, will be monitored and documented from the time of signing of informed consent at Screening until the EOS Visit (approximately 35 days after the EOT Visit). Participants should be instructed to report any AE that they experience to the Investigator, whether or not they think the event is due to study treatment. Beginning at the time of signing of informed consent, Investigators should make an assessment for AEs at each visit and record the event on the appropriate AE eCRF.

Wherever possible, a specific disease or syndrome rather than individual associated signs and symptoms should be identified by the Investigator and recorded on the eCRF. However, if an observed or reported sign or symptom is not considered a component of a specific disease or syndrome by the Investigator, it should be recorded as a separate AE on the AE eCRF. Additionally, the condition that led to a medical or surgical procedure (eg, surgery, endoscopy, tooth extraction, or transfusion) should be recorded as an AE, not the procedure itself.

Any medical condition already present at Screening should be recorded as medical history and not be reported as an AE unless the medical condition or signs or symptoms present at Baseline change in severity, frequency, or seriousness at any time during the study. In this case, it should be reported as an AE.

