3.5 Safety Assessment

Safety Population will be the primary population for the safety analyses. All safety endpoints will be summarized descriptively by treatment group and overall. No statistical inference will be applied to the safety endpoints.

3.5.1 *Adverse Events (AEs)*

AEs will be categorized by primary system organ class and preferred term as coded using the current MedDRA version category designation.

An overview of treatment-emergent AEs (TEAEs) will be provided including counts and percentages of participants with the following:

- Any TEAEs (overall and by maximum severity)
- Any TEAEs (non-serious)
- Any study drug related TEAEs (overall and by maximum severity)
- Any TEAEs leading to discontinuation of study drug
- Any treatment-emergent serious AEs (TESAEs)
- Any study drug related TESAEs
- Any TEAEs leading to death.

The TEAEs described above will be summarized separately by system organ class and preferred term. The non-serious TEAEs occurring in more than 2% of participants in any treatment group and preferred term will be summarized.

Listings will be presented specifically for TEAEs, TESAEs and TEAEs leading to discontinuation of study drug and TEAEs leading to death.

3.5.2 *Event of Special Interest*

Events of special interest (ESIs) include the following: hepatic abnormalities, muscle-related abnormalities, new-onset diabetes mellitus (NODM) and/or hyperglycemia, renal abnormalities, changes to antihypertensive medication(s) due to changes in blood pressure, and macular degeneration described as follows:

- AST or ALT > 3×ULN;
- Total bilirubin > 2×ULN;
- Creatine kinase (CK) > 5 × ULN;
- NODM or worsening of glycemic control;

Note: NODM is defined by 1 or more of the following criteria, based upon information from AE, medication, and laboratory data:

- AE indicating new type 1 or type 2 diabetes;

- Initiation of anti-diabetes medication with confirmation of the diagnosis of diabetes by blinded external review by experts in diabetology;
- HbA1c $\geq 6.5\%$ (≥ 0.065 hemoglobin fraction); and/or
- Two consecutive values of fasting plasma glucose that are ≥ 126 mg/dL (≥ 7.0 mmol/L).

Note: Worsening of glycemic control will be defined as HbA1c increase from Baseline $>0.5\%$ (>0.005 hemoglobin fraction) and/or a new concomitant medication or increase in current antidiabetic therapy in a participant with a Baseline HbA1c $\geq 6.5\%$ (≥ 0.065 hemoglobin fraction)

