Participants will be identified as those who had a diagnosis of hypertension in their medical history and received antihypertensive medication(s) at Baseline. If participants had an adverse event related to hypertension after Baseline (see [Appendix B](#) for preferred terms) and had any change in antihypertension medication within 30 days of the start date of the adverse event, that change

in antihypertension medication will be considered as due to a change in blood pressure. The number and percentage of participants will be summarized by treatment group.

Participants will be identified who did not have a prior diagnosis of hypertension in their medical history and did not receive antihypertensive medication(s) at Baseline. If participants had an adverse event of hypertension and initiated antihypertension medication within 30 days of the start date of the adverse event, the adverse event will be classified as a change in blood pressure. The number and percentage of participants will be summarized by treatment group.

Cases of macular degeneration will be recorded and summarized using the appropriate system organ class. These events will be summarized by severity and relationship to study drug for each treatment group.

3.5.3 *Clinical Laboratory Tests*

Blood and urine samples for clinical laboratory evaluations (including a full serum chemistry panel, hematology, coagulation, and urine dipstick analysis) will be collected at visits specified in [Table 1](#). A limited serum chemistry panel will also be collected as specified in Table 1. All safety laboratory samples should be collected while the participant is fasting (a minimum of 8 hours) and prior to the next dose of study drug (at applicable visits). Urinalysis will be performed locally by dipstick analysis from a sample of mid-stream urine. See clinical protocol ([Appendix B](#)) for a complete list of analytes.

Laboratory values will be summarized descriptively, including the change from Baseline. In addition, shift tables for all parameters will be presented to describe the change in laboratory parameter values at end of treatment visit using normal range categories (low, normal, and high).

Chemistry and hematology laboratory parameters will be listed.

3.5.4 *Vital Signs*

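### SAP 3.1.8 imputes partial AE start dates without reference to first dose, so a post-dose AE can be classed as pre-treatment and leave the TEAE tables

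*SAP*

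**What the plan says.** The rule is in SAP 3.1.8, under Date Values. It covers AE, medication and medical-history dates together. The principle is that "the missing component(s) will be assumed as the most conservative value possible". The illustration is that "if the start date is incomplete, the first day of the month will be imputed for the missing day", with January for a missing start month. Partial stop dates go to the last day of the month, or to December. The same section states the purpose: "Date imputation will only be used for computational purposes such as treatment-emergent status". First dose is not mentioned.

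Treatment-emergent status decides what appears in SAP 3.5.1: "An overview of treatment-emergent AEs (TEAEs) will be provided including counts and percentages of participants with the following". The system-organ-class and preferred-term summaries follow the same selection, and so do the AE listings: "Listings will be presented specifically for TEAEs, TESAEs and TEAEs leading to discontinuation of study drug and TEAEs leading to death".

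Protocol 8.1 says that AEs "will be monitored and documented from the time of signing of informed consent at Screening until the EOS Visit". The AE data therefore include pre-dose events, and the split at first dose has to be derived from dates. The SAP expands the abbreviation TEAE but gives no onset, worsening or end-of-window criterion. The protocol gives none either.

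**The concern.** For treatment-emergent status in a safety table, the conservative choice is to keep a doubtful AE in. Moving a partial start date to the earliest possible day does the opposite whenever the known part of the date is compatible with onset after dosing. The worked rule therefore conflicts with the principle it illustrates, for the one use that the section names.

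At stake is the count of AEs early in treatment. An event that truly began days after the first tablet would be treated as a screening event. It would be absent from the TEAE overview, from the tables by system organ class and preferred term, and from the TEAE listings.

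**Working it through.** The plan states no figure on this point, so there is nothing to reproduce. The check applies the SAP 3.1.8 rule literally to calendar dates.

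**Inputs**
- From SAP 3.1.8: missing day becomes the 1st; missing month becomes January.
- From Protocol 8.1: AEs are collected from consent to the EOS Visit. Day 365 plus about 35 days gives a post-dose span of about 400 days.
- Assumed: a TEAE has onset on or after first dose; first dose is equally likely on each of 365 days; the onset distribution is as stated below.

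**One case.** First dose 15 March, true onset 20 March, day missing. The imputed start is 1 March. Since 1 March precedes 15 March, the AE is not treatment-emergent.

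**How often this happens within the first-dose month.** It fails only to happen when dosing began on the 1st: (365 − 12)/365 = 353/365 = 96.7% of first-dose dates. If the month is also missing and the AE falls in the first-dose year, the figure is 364/365 = 99.7%.

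**Share of all day-missing post-dose AEs, uniform onset.** In a month of L days, a first dose on day d (d ≥ 2) leaves L − d + 1 onset days that will be misclassified. Summing over d gives L(L − 1)/2 per month. Over the year: 7 × 465 + 4 × 435 + 378 = 5,373. Averaged over first-dose dates: 5,373/365 = 14.7 days. As a share of 400 days: 14.7/400 = 3.7%, or about 4%. Over the 365-day treatment period alone it is 14.7/365 = 4.0%.

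**Front-loaded onset.** Weight day k after first dose (k = 0 to 399) by exp(−k/m), and average the weight falling in the first-dose month over all first-dose dates other than the 1st:

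| Assumed onset | Share classed as pre-treatment |
|---|---|
| Uniform over 400 days | 3.7% |
| m = 120 days | 11.7% |
| m = 60 days | 20.9% |
| m = 30 days | 36.1% |

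**Month also missing, uniform onset.** The misclassified days average (364 × 365/2)/365 = 182. As a share: 182/400 = 45.5%, or 182/365 = 49.9% over the treatment period alone. Such dates should be rare.

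**After the change proposed below.** Every compatible start date is moved no earlier than first dose, so none of the enumerated post-dose onsets is imputed before dosing.

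**Cost of the change.** Take a screening AE with onset k days before first dose (k = 1 to 14) and the day missing. It lies in the first-dose month for 365 − 12k of the 365 first-dose dates. Summing over k: (14 × 365 − 12 × 105)/(14 × 365) = 3,850/5,110 = 75.3%. These would be counted as TEAEs if no stop date excludes them.

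**The case against.** The strongest reply is that the conservative-value sentence governs and the first-of-month text is only an example, shared by three kinds of record. A programmer applying the principle would keep a doubtful AE as treatment-emergent. SAP 7 also mentions separate programming specifications, which may settle it. This stands in part: whether any AE would actually be lost cannot be known from these documents. But the example is the only operational rule given, it explicitly covers AE dates, and it points the wrong way for the use that the section names.

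The missing TEAE definition is fairly described as missing detail. SAP 3.1.1 and 3.3.6 anchor analysis day and concomitant medication to first dose, Protocol 8.7.4 ties its laboratory criteria to tests after first dose, and Protocol 8.1 makes worsening of a Baseline condition reportable as an AE. Analysts would probably fill the gap sensibly. The end of the window remains open.

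Safeguards also limit the effect. AEs are assessed at each visit, missing data are queried (Protocol 10.1.5), and SAEs are reported within 24 hours (Protocol 8.3).

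A reader might infer three stronger things that the documents do not support:
- **A material number of AEs lost.** No count of partial dates is given, so the shares above cannot be turned into numbers of events. SAP 3.5.1 also counts participants, so a lost AE changes a row only if that participant has no other qualifying event in it.
- **A biased comparison between arms.** Both arms follow the same rule, and SAP 3.5 applies no inference to safety.
- **A broken antihypertensive-change summary in SAP 3.5.2.** That rule does look for a participant who "had any change in antihypertension medication within 30 days of the start date of the adverse event", but SAP 3.1.8 does not say that imputed dates feed it. The 30-day gap is in any case a separate matter from the first-dose comparison.

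**Conclusion.** The point holds and is minor. Followed as written, and with a TEAE taken as onset on or after first dose, the worked rule misclassifies post-dose AEs with the day missing in the first-dose month, and those with the month also missing in the first-dose year. The size as a share of day-missing post-dose AEs depends on the assumed onset pattern: about 4% if uniform, 12% to 36% for assumed means of 120 to 30 days. The number of such AEs is not given and should be small, so the effect on any table row should be smaller still. Listings show the dates as collected, and SAP 7 provides for listing all available data. Efficacy is unaffected.

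**What to change.** Add to SAP 3.1.8, for AE start dates only:

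1. If the known part of the start date allows onset on or after first dose, and the stop date (by the current latest-day rule if partial) is not before first dose, impute the later of the current-rule date and the first-dose date.
2. Treat a completely missing start date as treatment-emergent unless the stop date precedes first dose.
3. Otherwise keep the current rule.

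As a clarification in SAP 3.5.1, define a TEAE (onset, or worsening of an existing condition, on or after first dose) and state where the window ends, given that collection runs to the EOS Visit.

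The cost is a few sentences and a standard programming rule, with no new data; it can be settled before database lock. The downside is that about 75% of screening AEs with the day missing and no excluding stop date would be counted as TEAEs, if onset is uniform over Days −14 to −1. That errs in the conservative direction for safety, which is what SAP 3.1.8 says it intends.

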3.2 Analysis Populations

3.2.1 *Intent-to-Treat (ITT) Population*

The ITT Population will include all participants who are randomized into the study. Treatment classification will be based on the randomized treatment.

3.2.2 *The Full Analysis Set (FAS)*

The FAS will include all participants who are randomized into the study, take any study drug, and have at least 1 post-treatment lipid data assessment. Treatment classification will be based on the randomized treatment.

3.2.3 *Modified Intent-to-Treat (mITT) Population*

The mITT Population will include all randomized participants who receive at least 1 dose of any study drug and have data for both the Day 1 and Day 84 LDL-C assessments. Treatment classification will be based on the randomized treatment.

3.2.4 *Modified Intent-to-Treat (mITT) On-Treatment Population*

The mITT On-Treatment Population will include all randomized participants who have data for both the Day 1 and Day 84 LDL-C assessments. Participants in the obicetrapib group with PK values less than 3 standard deviations from the mean obicetrapib concentration should be excluded. Treatment classification will be based on the randomized treatment.

Rationale: in previous studies, such as ROSE (protocol number TA-8995-201), TULIP (protocol number TA-8995-03), and ROSE2 (protocol number TA-8995-202), it was demonstrated that the minimally observed obicetrapib concentration for C_{max} was less than three standard deviations from the mean at respectively Week 4 and Week 12 [3-5].

3.2.5 *Per-Protocol (PP) Population*

The PP Population will include all participants in the mITT Population who did not experience a major protocol deviation that potentially impacted the primary efficacy endpoint. The PP Population, along with the reason for exclusion, will be finalized prior to study unblinding.

3.2.6 *Safety Population*

The Safety Population will include all participants who receive at least 1 dose of any study drug. Treatment classification will be based on the actual treatment received. The Safety Population will be the primary population used for the safety analyses.

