7. A single 12-lead ECG will be performed in the supine position after 10 minutes of rest.
8. Participants must fast for a minimum of 8 hours prior to samples being collected.
9. Samples should be collected prior to study drug administration.
10. Urinalysis will be performed locally by dipstick analyses from a sample of mid-stream urine. In case of abnormal results, microscopy and other assessments will be performed at the local laboratory and the abnormality recorded as an AE.
11. A PK sample will be collected prior to study drug administration for trough measurement of obicetrapib in plasma. At Visits 2, 5, and 7, participants should take study drug after a trough PK sample has been drawn.
12. The PK sample at Visit 4 is not designated in the protocol, however the PK will be assessed using residual serum from the Day 84 limited chemistry panel to confirm patients are taking IP.

AE = adverse event; ApoA1 = apolipoprotein A1; BMI = body mass index; CV = cardiovascular; ECG = electrocardiogram; EOS = End of Study; EOT = End of Treatment; ET = Early Termination; FSH = follicle-stimulating hormone; hsCRP = high sensitivity C-reactive protein; Lp(a) = lipoprotein (a); PK = pharmacokinetic(s); TSH = thyroid-stimulating hormone; UACR = urine albumin-creatinine ratio; UPCR = urine protein-creatinine ratio; V = Visit.

2.2.2 *Sample Size Determination*

Enrollment of approximately 300 participants globally is planned for this study.

Assuming an approximate 5% drop out rate, approximately 285 participants will be evaluable for efficacy. This sample size of at least 285 evaluable participants will provide more than 90% power to detect a 30% reduction of LDL-C (standard deviation 15%) levels in the obicetrapib group compared to the placebo group at a 1-sided significance level of 0.025. This sample size will also contribute to sufficient participant exposure and safety data.

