3.3.7 Study Drug Exposure and Compliance

Participants' exposure to randomized study drug will be summarized with descriptive statistics for the Safety Population and mITT On-Treatment Population. Days of exposure to study drug will be calculated as

$$\text{date of last dose of study drug} - \text{date of first dose of study drug} + 1.$$

For participants' whose date of first dose from the initial bottle dispensed was not available, the date of randomization will be used to assign the date of first dose. For participants who failed to provide the date of last dose of study drug, the earliest date between the end of treatment date and the date of the end of study/early termination will be used.

Days of exposure to study drug will be summarized by treatment group based on the Safety Population with counts and percentages of participants with exposure in the following categories:

- <3 weeks
- 3 – <5 weeks
- 5 – <7 weeks
- 7 – <9 weeks
- 9 – <11 weeks
- 11 – <13 weeks
- 13 – <19 weeks
- 19 – <25 weeks
- 25 – <28 weeks
- 28 – <34 weeks
- 34 – <40 weeks
- 40 – <50 weeks
- 50 – <54 weeks
- >=54 weeks

The percentage overall compliance to study drug will be calculated using the following formula:

$$\frac{\# \text{ tablets dispensed} - \# \text{ tablets returned}}{\# \text{ expected dosing days}} \times 100$$

If study drug is not returned, the number of tablets returned and lost will be considered 0 for the compliance calculation. The expected dosing days will be calculated as the earliest date between the end of treatment date and the date of early termination – the date of randomization- missed doses+1 (*missed doses defined as number of doses missed during IP interruptions due to AE or IP interruptions that are longer than 14 days*).

Percent compliance to the study drug regimen will be summarized by treatment group and in total based on the Safety Population and mITT On-Treatment with descriptive statistics and with counts and percentages of participants with compliance in the following categories:

- <80%
- 80% to 120%
- >120%

Study drug interruptions due to AE or IP interruptions longer than 14 days will be listed.

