3.4 Efficacy Assessment

The ITT Population will be the primary population for the efficacy analysis. Efficacy will also be analyzed in the FAS, mITT Population, mITT On-Treatment Population, and PP Population as supportive analyses.

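### Read literally, SAP 3.2.4 drops obicetrapib participants with typical drug levels from the mITT On-Treatment Population; the PK visit, scale and reference values are also undefined (supportive analyses only)

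*SAP*

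**What the plan says.** SAP 3.2.4 starts from randomized participants with LDL-C data at Day 1 and Day 84, and then adds: "Participants in the obicetrapib group with PK values less than 3 standard deviations from the mean obicetrapib concentration should be excluded". The rationale in the same section says that in three earlier obicetrapib studies the lowest observed Cmax "was less than three standard deviations from the mean at respectively Week 4 and Week 12".

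SAP Table 1 (Section 2.2.1) schedules PK at Days 1, 84, 180 and 365 and at the End of Study Visit. Its footnotes describe the samples:

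- Footnote 11, scheduled PK: "A PK sample will be collected prior to study drug administration for trough measurement of obicetrapib in plasma".
- Footnote 9, which covers the PK and chemistry samples: "Samples should be collected prior to study drug administration".
- Footnote 12, Day 84, which was not a PK visit in the protocol: "the PK will be assessed using residual serum from the Day 84 limited chemistry panel to confirm patients are taking IP".

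The population is used in these places:

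- Efficacy (3.4), in the list that ends "mITT On-Treatment Population, and PP Population as supportive analyses".
- The supplemental ANCOVA and the supplementary analysis of the secondary estimand (3.4.1).
- Exposure (3.3.7), "summarized with descriptive statistics for the Safety Population and mITT On-Treatment Population", and compliance (3.3.7), "in total based on the Safety Population and mITT On-Treatment".
- Demographic and baseline summaries, if the set differs from ITT (3.3.4).

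Section 5.2 finalizes exclusions from the analysis populations before treatment assignments are unblinded.

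**The concern.** A value less than 3 SD from the mean is, in plain English, a value close to the mean. Applied as written, the rule discards ordinary takers of obicetrapib and retains the unusual values. The population's name and footnote 12 point the other way: the evident aim is to set aside participants whose drug level suggests that they were not taking study drug.

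Correcting the direction does not complete the rule. A programmer must still decide which visit's PK value counts, whether to work on the raw or the log scale, and whether the mean and SD come from this trial or from earlier ones. Two programmers could build different sets, and those choices could be made after unblinding. Non-takers left in the set would also pull an on-treatment estimate toward zero. If they respond like placebo, each 1% left in costs 30 x 0.01 = 0.3 points of the planned 30-point difference.

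**Working it through.** **Inputs.** From SAP 2.2.2 and 2.2.1: about 300 randomized 2:1, 5% dropout, planned difference 30 points, SD 15. The documents give no count for this population, no CV for obicetrapib concentrations and no number of non-takers. Those used below are assumptions.

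**1. The plan's own figure.** 300 x 0.95 = 285 evaluable, as stated. Split 2:1, this gives 190 obicetrapib and 95 placebo. Power for 30 points (SD 15, 1-sided 0.025) is essentially 1, consistent with the stated figure of more than 90%.

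**2. Rule and rationale side by side.**

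| Reading of the phrase | Rule | Rationale |
|---|---|---|
| Within 3 SD of the mean | Excludes typical takers | Makes sense: the lowest treated values lay inside 3 SD |
| Below mean minus 3 SD | Makes sense: excludes very low values | Contradicts the rule: the lowest values in treated participants would have failed it |

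No single reading makes both sentences work, and no other section gives a corrected rule.

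**3. Literal rule, with mean and SD from the same n values.** The squared deviations sum to (n-1)s². If k values lie 3 SD or more from the mean, then 9k ≤ n-1.

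- n = 190: k ≤ 189/9 = 21, so at least 190 - 21 = 169 are excluded.
- n = 180: k ≤ 179/9, so at most 19 are kept and at least 161 excluded.

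This holds for any distribution. It does not hold if the mean and SD come from other studies.

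The bound is generous. In lognormal simulation (4,000 trials per setting, n = 190, no non-takers) the average number kept is 1.2, 1.8, 2.3 and 2.8 at CV 20, 30, 40 and 50%.

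**4. Which outliers are kept.** Let a share f have zero concentration and let takers have CV c. The overall mean is then (1-f) and the variance (1-f)(c²+f), in units of the takers' mean. A zero lies (1-f)/√[(1-f)(c²+f)] SD below the mean. With 4 non-takers, f = 4/190:

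| CV | Distance of a zero from the mean | Literal rule |
|---|---|---|
| 20% | 4.0 SD | Keeps all 4 non-takers and on average 0.4 of 186 takers |
| 30% | 2.97 SD | Borderline: keeps a zero in some samples and drops it in others |
| 40% | 2.3 SD | Drops all 4; only about 2 takers remain, all high outliers |

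**5. Direction corrected, raw scale.** The cut-off is mean x (1-3c): 0.40, 0.10, 0 and -0.20 of the mean at CV 20, 30, 33.3 and 40%.

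If non-takers enter the mean and SD, a positive cut-off needs (1-f) > 9(c²+f), that is f < (1-9c²)/10. This gives 6.4% at CV 20% and 1.9% at CV 30%. In simulation at CV 20%, 9.9 of 10 non-takers are caught but 0 of 19. At CV 30%, 0 of 10 are caught.

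**6. Direction corrected, log scale.** Mean minus 3 SD on the log scale corresponds to exp(-3√ln(1+c²)) of the geometric mean: 0.55, 0.41, 0.31 and 0.24 at CV 20, 30, 40 and 50%. It is always positive.

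**7. Reference values.** The rationale rests on Cmax, while the samples here are pre-dose. Scheduled PK is plasma, while Day 84 is residual serum. Reference values from other sampling times or matrices may not transfer.

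**The case against.** The strongest reply is that this is a drafting slip with an obvious intent. The name, the rationale and footnote 12 all suggest that values more than 3 SD below the mean were meant. Counts per population are tabulated by arm (3.3.3), detailed programming specifications are a separate document (Section 7), and a set with two or three active participants would be noticed. This largely stands as a comment on likelihood, so nearly empty tables are not the probable outcome. It does not supply the visit, the scale or the reference, and the rationale still contradicts the intended rule.

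A reader might infer more than the documents support on four points:

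- *That the rule always keeps non-takers.* It does so only at low CV with few non-takers. At CV 40% or more it drops them.
- *That 169 excluded is a fact about the trial.* It needs 190 PK values and an in-sample mean and SD. The SAP names no source, and its rationale points to earlier studies.
- *That 3.2.4 contradicts its own stated purpose.* It states none. The purpose is inferred from the name, the rationale and a footnote that does not cite 3.2.4.
- *That lost precision is the harm.* Even at 21 against 95, the standard error is 15√(1/21+1/95) = 3.62 points, against 15√(1/190+1/95) = 1.88. A 30-point difference is still 30/3.62 = 8.3 standard errors. The harm lies in who is kept.

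**Conclusion.** The exclusion rule is wrong as written and should be corrected. The finding that rule and rationale cannot both work under one reading rests on the text alone. The size, at least 169 of 190 excluded, depends on the conditions set out in the working. The possibility that a corrected raw-scale rule excludes nobody is conditional on a CV that the documents do not give; at low CV with few non-takers the corrected rule would work.

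The reach is limited to supportive efficacy, the supplemental ANCOVA, the supplementary analysis of the secondary estimand, exposure and compliance, and baseline summaries where the set differs from ITT. A reader might infer that the primary result is at risk. It is not: the primary analysis uses the ITT Population, which this rule does not touch.

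**What to change.** Reword 3.2.4 so that obicetrapib participants whose PK value at a named visit is **below** a numeric floor fixed before database lock are excluded. In detail:

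- **Visit.** Name it. Day 84 is the natural choice because it matches the endpoint and footnote 12, but it is a choice that the SAP has not yet made.
- **Floor.** Use one that cannot be negative. One reasonable option is the log-scale mean minus 3 SD from earlier data of comparable sampling time and matrix. If no such data exist, use the assay's lower limit of quantification.
- **Missing PK.** State how participants without a result at that visit are handled, and report their number.
- **Section 5.2.** The rule needs arm membership, but exclusions are finalized before unblinding. Say that this fixed rule is applied programmatically after unblinding, without discretion.
- **Rationale.** Reword it so that it no longer conflicts with the rule, and address Cmax against pre-dose sampling and plasma against serum.

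The cost is SAP wording only, since the Day 84 assay is already planned. The set may be slightly smaller, and it is selected on drug level in one arm only, which should be stated when results are reported. With the quantification-limit floor, partial takers with measurable drug stay in.
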